## 9.1 Statistical Analysis Plan Summary

Key elements of the statistical analysis plan are summarized below; the comprehensive plan is provided in Sections 9.2 to 9.12.

Study Design Overview	A Phase 3, multicenter, randomized, double-blind study of MK-7684 with pembrolizumab as a coformulation (MK-7684A) versus pembrolizumab monotherapy as first line treatment for participants with PD-L1 positive (TPS $\geq 1\%$ ) metastatic NSCLC (KEYVIBE-003)
Treatment Assignment	Approximately 1246 participants will be randomized in a 1:1 ratio between treatment groups: (1) MK-7684A (2) pembrolizumab. Stratification factors are: 
 
• ECOG PS (0 versus 1)
 
• PD-L1 TPS (1% to 49% versus <math>\geq 50\%</math>)
 
• Region: East Asia vs Non-East Asia
 

Analysis Populations	Efficacy: ITT Safety: APaT PRO: PRO FAS
Primary Endpoints	
 
• OS in participants with PD-L1 TPS <math>\geq 50\%</math>
 

Secondary Endpoints	

• OS in participants with PD-L1 TPS <math>\geq 1\%</math> and PD-L1 TPS 1% to 49%

• PFS per RECIST 1.1 as assessed by BICR in participants with PD-L1 TPS <math>\geq 50\%</math>, PD-L1 TPS <math>\geq 1\%</math> and PD-L1 TPS 1% to 49%

• OR per RECIST 1.1 as assessed by BICR in participants with PD-L1 TPS <math>\geq 50\%</math>, PD-L1 TPS <math>\geq 1\%</math> and PD-L1 TPS 1% to 49%

• DOR per RECIST 1.1 as assessed by BICR in participants with PD-L1 TPS <math>\geq 50\%</math>, PD-L1 TPS <math>\geq 1\%</math> and PD-L1 TPS 1% to 49%

• ePROs: global health status/QoL score, physical functioning score, role functioning score, and dyspnea score using EORTC QLQ C30 and cough and chest pain scores using EORTC QLQ-LC13 in participants with PD-L1 TPS <math>\geq 50\%</math>, PD-L1 TPS <math>\geq 1\%</math> and PD-L1 TPS 1% to 49%

• Safety and tolerability

Statistical Methods for Key Efficacy Analyses	
The primary hypotheses testing for OS and the secondary hypotheses testing for PFS and OS will be evaluated by comparing the MK-7684A group to the pembrolizumab group using CCI [REDACTED]. The HR will be estimated using a CCI [REDACTED]. Event rates over time will be estimated within each treatment group using the Kaplan-Meier method. CCI [REDACTED]

Statistical Methods for Key Safety Analyses	
For analyses in which 95% CIs will be provided for between-treatment differences in the percentage of participants with events CCI [REDACTED]

Interim Analyses	
CCI [REDACTED]

Multiplicity	CCI
Sample Size and Power	

## 9.2 Responsibility for Analyses/In-house Blinding

The statistical analysis of the data obtained from this study will be the responsibility of the Clinical Biostatistics Department of the Sponsor.

This study will be conducted as a double-blind study under in-house blinding procedures. The official, final database will not be unblinded until medical/scientific review has been performed, protocol deviations have been identified, and data have been declared final and complete.

The Sponsor will generate the randomized allocation schedule(s) for study treatment assignment. Randomization will be implemented in an IRT.

Key aspects of blinding during interim analyses are described in Section 9.7.

## 9.3 Hypotheses/Estimation

Objectives and hypotheses of the study are stated in Section 3.

## 9.4 Analysis Endpoints

Efficacy and safety endpoints that will be evaluated for within- and/or between-treatment differences are listed below, followed by the descriptions of the derivations of selected endpoints.

### 9.4.1 Efficacy Endpoints

#### Primary

- **Overall Survival (OS)**

OS is defined as the time from randomization to death due to any cause.

#### Secondary

- **Progression-free survival (PFS)**

PFS is defined as the time from randomization to the first documented disease progression per RECIST 1.1 by BICR or death due to any cause, whichever occurs first.

- **Objective Response (OR)**

OR is defined as a confirmed CR or PR per RECIST 1.1 based on BICR.

- **Duration of Response (DOR)**

For participants who demonstrate confirmed CR or PR, DOR is defined as the time from the first documented evidence of CR or PR until disease progression or death due to any cause, whichever occurs first.

### 9.4.2 Safety Endpoints

Key safety endpoints are AEs and study treatment discontinuations due to AEs. In addition, safety parameters commonly used for evaluating investigational systemic anticancer treatments, including but not limited to all AEs, SAEs, fatal AEs, and laboratory changes, will be evaluated by clinical review. AEs will be assessed as defined by NCI CTCAE, Version 5.0. A description of safety measures is provided in Section 8.3.

### 9.4.3 PRO Endpoints

Key PRO endpoints include the following:

- Change from baseline in EORTC QLQ-C30 global health status/QoL score, physical functioning score, role functioning score, dyspnea score, and EORTC QLQ-LC13 cough and chest pain scores.
- TTD as measured by EORTC QLQ-C30 global health status/QoL score, physical functioning score, role functioning score, dyspnea score, and EORTC QLQ-LC13 cough and chest pain scores.

Based on prior literature [Bjordal, K., et al 2000] [Osoba, D., et al 1998] [King, M. T. 1996], a 10-point or greater worsening from baseline for each scale represents a clinically relevant deterioration. TTD is defined as the time to first onset of 10 or more (of 100) deterioration

from baseline in a given scale/subscale/item and confirmed by a second adjacent 10 or more deterioration from baseline. If the first deterioration is at the last PRO assessment timepoint (in the current database lock), then no confirmation is required.

CCI

Details regarding PRO endpoints will be provided in the sSAP.

## **9.5 Analysis Populations**

### **9.5.1 Efficacy Analysis Populations**

The analyses of the efficacy endpoints are based on the ITT population. All randomized participants will be included in this population. Participants will be analyzed in the treatment group to which they are randomized. Details on the approach to handling missing data are provided in Section 9.6.1.5.

### **9.5.2 Safety Analysis Populations**

The APaT population will be used for the analysis of safety data in this study. The APaT population consists of all randomized participants who received at least one dose of study treatment. Participants will be analyzed in the treatment group corresponding to the study treatment they actually received. For most participants, this will be the treatment group to which they are randomized. Participants who take incorrect study treatment for the entire treatment period will be included in the treatment group corresponding to the study treatment actually received.

At least one laboratory measurement obtained subsequent to at least one dose of study treatment is required for inclusion in the analysis of each specific parameter. To assess change from baseline, a baseline measurement is also required.

### **9.5.3 Patient-reported Outcome Analysis Population**

The PRO analyses are based on the PRO FAS population, defined as all randomized participants who have at least one PRO assessment available for the specific endpoint and have received at least one dose of the study intervention. Participants will be analyzed in the treatment group to which they are randomized.

## **9.6 Statistical Methods**

Statistical testing and inference for safety analyses are described in Section 9.6.2. Efficacy results that will be deemed to be statistically significant after consideration of the Type I error control strategy are described in Section 9.8. Nominal p-values may be computed for other efficacy analyses, but should be interpreted with caution due to potential issues of multiplicity, sample size, etc.

Participants will be categorized into PD-L1 TPS groups based on stratification level at randomization.

### 9.6.1 Statistical Methods for Efficacy Analyses

This section describes the statistical methods that address the primary and secondary objectives. Methods related to exploratory objectives will be described in the sSAP.

The stratification factors used for randomization (see Section 6.3.2) will be applied to all stratified analyses, in particular, CCI [REDACTED]

[REDACTED] In the event that there are small strata, for the purpose of analysis, strata will be combined to ensure sufficient number of participants, responses and events in each stratum. Details regarding the pooling strategy will be prespecified in the sSAP prior to the database lock for the first efficacy interim analysis, and decisions regarding the pooling will be based on a blinded review of response and event counts by stratum.

The efficacy analyses for PFS, OR, and DOR will include documented progression events and responses that occur prior to Second Course treatment.

#### 9.6.1.1 Overall Survival (OS)

The nonparametric Kaplan-Meier method will be used to estimate the overall survival curves in each treatment group. CCI [REDACTED]

[REDACTED] The stratification factors used for randomization (see Section 6.3.2) will be applied to both the stratified log-rank test and the stratified Cox model. Participants without documented death at the time of analysis will be censored at the date the participant was last known to be alive. Additional supportive unstratified analyses may also be provided.

#### 9.6.1.2 Progression-free Survival (PFS)

The nonparametric Kaplan-Meier method will be used to estimate the PFS curve in each treatment group. CCI [REDACTED]

Since disease progression is assessed periodically, PD can occur any time in the time interval between the last assessment where PD was not documented and the assessment when PD is documented. The true date of disease progression will be approximated by the earlier of the date of the first assessment at which PD is objectively documented per RECIST 1.1 by BICR and the date of death. Death is always considered a PD event.

CCI

### 9.6.1.3 Objective Response Rate (ORR)

The stratified Miettinen and Nurminen's method will be used for the comparison of ORR between 2 treatment groups. The difference in ORR and its 95% CI from the CCI [REDACTED] will be reported. The stratification factors used for randomization (see Section 6.3.2) will be applied to the analysis. The point estimate of ORR will be provided by treatment group, together with 95% CI using CCI [REDACTED]

### 9.6.1.4 Duration of Response (DOR)

If sample size permits, DOR will be summarized descriptively using Kaplan-Meier medians and quartiles. Only the subset of participants who show a confirmed CR or PR will be included in this analysis. CCI [REDACTED]

CCI [REDACTED]

### 9.6.1.5 Analysis Strategy for Key Efficacy Variables

A summary of the primary analysis strategy for the key efficacy endpoints is provided in [Table 10](#).

Table 10 Analysis Strategy for Key Efficacy Variables

[figure not shown]
Endpoint/Variable	Statistical Method	Analysis Population	Missing Data Approach
Primary Analyses			
OS	CCI	ITT (participants with PD-L1 TPS ≥50%)	Censored at the date participant last known to be alive
Key Secondary Analyses			
OS	CCI		Censored at the date participant last known to be alive
PFS per RECIST 1.1 by BICR	CCI		Censored according to rules in Table 8
ORR per RECIST 1.1 by BICR	CCI		Participants with missing data are considered nonresponders
BICR = blinded independent central review; ITT = intent-to-treat; ORR = objective response rate; OS = overall survival; PFS = progression-free survival; RECIST 1.1 = Response Evaluation Criteria in Solid Tumors.			

**9.6.2 Statistical Methods for Safety Analyses**

The primary safety analyses will include only events that occur prior to Second Course Treatment.

The overall safety evaluation will include a summary by treatment group of the number and percentage of participants with at least one AE, drug-related AE, serious AE, serious drug-related AE, Grade 3-5 AE, discontinuation from study intervention due to an AE, and an AE resulting in death. Only point estimates by treatment group are provided.

CCI

CCI

CI for between treatment group differences will be provided using the M&N method [Miettinen, O. and Nurminen, M. 1985]. Because many 95% CIs may be provided without adjustment for multiplicity, the CIs should be regarded as a helpful descriptive measure to be used in safety review, not as a formal method for assessing the statistical significance of the between-group differences (Table 11).

CCI

### 9.6.3 Statistical Methods for Patient-Reported Outcome Analyses

This section describes the planned analyses for the PRO endpoints.

#### **Change from baseline**

The time point for the change from baseline will be determined based on blinded data review prior to the database lock for any PRO analysis and documented in the sSAP.

To assess the treatment effects on the PRO score, change from baseline in the global health status/QoL, physical functioning, role functioning, dyspnea, cough, chest pain, and, EQ-5D-5L VAS outcome a constrained longitudinal data analysis model proposed by Liang and Zeger [Liang, K-Y. and Zeger, S. L. 2000] will be applied, with the PRO score as the response variable, and treatment, time, the treatment by time interaction, and stratification

factors used for randomization (see Section 6.3.2) as covariates. The treatment difference in terms of LS mean change from baseline will be estimated from this model together with 95% CI. Model-based LS mean with 95% CI will be provided by treatment group for PRO scores at baseline and postbaseline time point.

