## 9 KEY STATISTICAL CONSIDERATIONS

Upon receipt of investigator letter detailing discontinuation of the MK-7684A clinical program, the following changes apply. The changes listed below supersede any protocol content/instructions from previous amendments.

- This study is closed to enrollment. This study has enrolled 1264 participants.
- This study will be unblinded.
- The estimated duration of study was updated from 6 years to 5 years.
- Participants receiving MK-7684A will be transitioned to pembrolizumab.
- Pembrolizumab can be sourced locally or centrally.
- Participants with access to approved SOC (eg, immunotherapy, chemotherapy, targeted therapy, as monotherapy or in combination) should be considered for discontinuation from the study. Those benefiting from pembrolizumab with, but unable to access it as SOC outside the study, may continue on study and receive treatment with pembrolizumab until discontinuation criteria are met. The final required study visit will be the Safety Follow-up Visit.
- Imaging scans should no longer be submitted to iCRO nor read by BICR. However, for participants who are still on study treatment and deriving clinical benefit and will continue study treatment until criteria for discontinuation are met, local tumor imaging should continue per local SOC schedule and local SOC method of assessment of imaging. All imaging as well as relevant objectives and endpoints will be assessed locally.
- PK/ADA samples will no longer be collected.
- Biomarker FBR samples will no longer be collected.
- ePROs will no longer be collected.
- Treatment beyond progression will no longer be offered. Any participant already receiving treatment beyond progression will be able to complete treatment as planned.
- Participants who complete study treatment or otherwise meet EOT criteria will be discontinued from the study after the EOT visit and any required safety follow-up visit.
- The futility interim analysis (IA1) was conducted. The pre-specified efficacy interim analysis (IA2) and final analysis outlined in the SAP will not be conducted.
- Selected analyses of safety and endpoints will be performed at the end of the study.
- There will be no follow-up for survival status. Participants currently in imaging follow up should obtain imaging and further oncological care as per local standard of care. However, standard safety reporting should continue, as applicable.

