- Those participants remaining on study at the time of Amendment 06 should continue to be monitored in the study through the AE reporting period (Section 8.4).

- Participants may enroll in an extension study, if available.
  - Participation in this study is ended when the participant is consented for an extension study.
  - The overall study ends when the last participant completes the last study-related contact, withdraws consent, or is lost to follow-up (Section 7.3), or the last participant on active treatment is consented in an extension study
  - For participants who enter an extension study, all AEs, SAEs, and other reportable safety events must be reported by the investigator in this protocol (parent study) from the time of intervention randomization up to the time of providing documented informed consent for an extension study. Note: Once consented to an extension study, safety events, including those considered related to study intervention, will be collected as instructed in the extension study.

Existing protocol content is retained for historical reference.

This section outlines the statistical analysis strategy and procedures for the study. If, after the study has begun, but prior to any unblinding/final database lock, changes are made to primary and/or key secondary hypotheses, or the statistical methods related to those hypotheses, then the protocol will be amended (consistent with ICH Guideline E-9). Changes to exploratory or other nonconfirmatory analyses made after the protocol has been finalized, but prior to unblinding/final database lock, will be documented in a supplemental SAP (sSAP) and referenced in the Clinical Study Report (CSR) for the study. Post hoc exploratory analyses will be clearly identified in the CSR. Separate analysis plans (ie, separate documents from the sSAP) will be developed to detail PK and biomarker analyses. The ePRO analysis plan will be included in the sSAP.

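### Does the PRO change-from-baseline model in Section 9.6.3 drop the common-baseline constraint that its name promises?

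*Combined protocol and SAP*

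**What the plan says.** Section 9.6.3 (Change from baseline) applies "a constrained longitudinal data analysis model", with a citation to the methods paper that proposed it. It describes the model "with the PRO score as the response variable, and treatment, time, the treatment by time interaction, and stratification" factors as covariates. The target is the difference between arms in LS mean change from baseline, with a 95% CI. It adds that "Model-based LS mean with 95% CI will be provided by treatment group for PRO scores at baseline and postbaseline time point", which shows that baseline belongs to the response vector.

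The rest of the PRO plan is placed elsewhere. Section 9.4.3 says "Details regarding PRO endpoints will be provided in the sSAP", and Section 9 says "The ePRO analysis plan will be included in the sSAP". Section 9 also provides that changes to nonconfirmatory analyses made "prior to unblinding/final database lock, will be documented in a supplemental SAP (sSAP"). The sSAP is not among the documents.

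The Amendment 06 list at the start of Section 9 states "ePROs will no longer be collected" and "Selected analyses of safety and endpoints will be performed at the end of the study". It cancels IA2 and the final analysis, and says that the older protocol text is kept only as a historical record.

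**The concern.** In a constrained longitudinal model the baseline score is part of the response and both arms share one baseline mean, because randomization makes the expected baseline difference zero. Treatment then enters only at post-baseline times. The list in Section 9.6.3 contains a treatment main effect and an unrestricted treatment-by-time interaction. Entered as they stand, these terms leave the baseline difference between arms free, so the constraint is lost. Nowhere does the protocol say that treatment acts only after baseline, and the promise of baseline LS means by arm could suggest that two separate baseline means are intended.

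Two analysts could therefore fit different models and report different estimates and interval widths for a listed secondary objective (Section 3). What is at stake is precision, and how far a chance baseline imbalance carries into the estimate.

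**Working it through.** **Inputs.** From the documents: 1:1 randomization and about 1246 participants planned (Section 9.1), so 623 per arm if all contribute. The documents give no SD, no baseline-to-follow-up correlation ρ, no dropout rate and no stated precision for this analysis, so there is no figure of the plan's to reproduce. Assumed: ρ from 0.3 to 0.8, and an SD of 25 points where a points scale is needed.

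**Do the two readings differ?** Yes. With baseline and six post-baseline visits, the literal terms use 14 arm-by-time mean parameters; the constrained model uses 13. The one removed is the baseline difference between arms.

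**Size with baseline and one later time point, equal SDs, complete data** (variances in SD² units, n per arm):

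- literal: (2/n) × 2(1 − ρ)
- constrained: (2/n) × (1 − ρ²)
- variance ratio, literal to constrained: 2/(1 + ρ), so the constraint lowers the variance by (1 − ρ)/2, whatever n is.

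At n = 623 and ρ = 0.3, the literal SE is √(2 × 1.4/623) = 0.0670 and the constrained SE is √(2 × 0.91/623) = 0.0540. The half-width in points is 1.96 × 25 × SE.

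| ρ | Variance reduction | SE literal | SE constrained | 95% half-width, literal / constrained (points) |
|---|---|---|---|---|
| 0.3 | 35% | 0.0670 | 0.0540 | 3.28 / 2.65 |
| 0.55 | 22.5% | 0.0538 | 0.0473 | 2.63 / 2.32 |
| 0.8 | 10% | 0.0358 | 0.0340 | 1.76 / 1.67 |

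**Unequal SDs.** With k the ratio of post-baseline to baseline SD, the literal variance is proportional to 1 + k² − 2ρk and the constrained variance to k²(1 − ρ²). At k = 1.2, ρ = 0.8 these are 0.5200 and 0.5184, a reduction of 0.3%. At k = 0.8, ρ = 0.3 they are 1.1600 and 0.5824, a reduction of 50%.

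**Dropout.** With six post-baseline visits, 40% retention at the last visit and SD 25, generalized least squares gives SEs (literal, constrained) of 2.298 and 2.073 at ρ = 0.3, 1.967 and 1.835 at 0.5, and 1.538 and 1.478 at 0.7. The literal SE is 11%, 7% and 4% larger. The half-width differs by 1.96 × 0.225 = 0.44, 1.96 × 0.132 = 0.26 and 1.96 × 0.060 = 0.12 points.

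**Bias and imbalance.** Averaged over randomization neither model is biased: a simulation of 4000 trials at ρ = 0.5 gave mean errors of 0.01 (literal) and 0.03 (constrained) points and an SE ratio of 1.148. Given an observed baseline difference d, the literal estimate shifts by −(1 − ρ)d. The SD of d is 25 × √(2/623) = 1.42 points, so a one-SD imbalance moves the literal estimate by about 0.99 points at ρ = 0.3 and 0.28 at ρ = 0.8. The literal interval already allows for this; that is why it is wider.

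**Which reading does the text support?** The method is given by name and by citation, and the equal-baseline constraint is what the word constrained refers to. The items that follow are presented as covariates. Treatment, time and their interaction are also the ingredients of the constrained model; the list does not say how they are coded at baseline, and it does not say that baseline means are free. By-arm baseline LS means do not decide the matter, since a constrained fit can report its common value under both arm headings.

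**The case for a change.** The best case for a change is that a plan should not need its method name to correct its term list. Section 9.1 calls Sections 9.2 to 9.12 the comprehensive plan, and a programmer working from the list alone would fit the wrong model. PRO change remains a secondary objective, 1264 participants were enrolled, and questionnaires were scheduled at every cycle through Cycle 17. The study is to be unblinded, so an open choice could be settled with results by arm in view. One sentence would close it.

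Part of this stands. The list does not state the constraint, and the algebra showing that the literal terms omit it is correct. The worry about a late choice carries less weight: the named method already points to one of the two models, both target the same treatment difference, and no test of H1 to H6 depends on the answer. The constraint also assumes equal expected baseline means in the PRO FAS, which Section 9.5.3 limits to participants with a dose and at least one PRO assessment. Under double-blind dosing that is a mild assumption.

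**Conclusion.** No change is needed. Section 9.6.3 prescribes the constrained model by name and reference, and its term list is abbreviated. An analyst following the plan would impose the common baseline mean, and the way the terms are coded is the kind of detail that the protocol assigns to the sSAP.

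If someone did fit the literal terms, the result would be unbiased with valid coverage but less precise. The documents do not fix how much less: the constraint lowers the variance by anything from 0.3% to 50% over the assumed correlations and SD ratios. On an assumed SD of 25 points, the half-width differs by about 0.1 to 0.6 points at 623 per arm. For scale, Section 9.4.3 treats a 10-point worsening within a participant as clinically relevant, although that is not a margin between arms. In the PD-L1 subsets n is smaller and the difference in points larger, but with complete data the relative loss does not depend on n.

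The practical consequence is close to nil. None of H1 to H6 concerns a PRO, ePRO collection has ended, IA2 and the final analysis are cancelled, and Section 9.6.3 survives as historical text. The question arises only if PRO change is among the selected end-of-study analyses, and the name of the method then answers it.
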